Continuous glucose monitors (CGMs) were originally designed for use in the home and outpatient setting, with less data on its application in the hospital or critical care settings. Until April 2020, CGMs were not approved for inpatient use. To support COVID-19 healthcare efforts, the FDA allowed for the use of continuous glucose monitoring (CGM) systems for the treatment of patients in various healthcare facilities. This remote glucose monitoring allowed for conservation of personal protective equipment (PPE) and reduction of potential exposure of staff from multiple point-of-care glucose checks. Compared to the POC checks every one to two hours, CGM systems can provide blood glucose readings multiple times each hour, allowing for remote monitoring and the ability to detect urgent changes in blood glucose.

Several studies have evaluated the use of CGM among hospitalized patients with DM and have shown positive results when compared to traditional POC glucose

monitoring. Most studies have found the use of CGM can help minimize the number of hypoglycemia episodes and overall improve patient care. Similar studies have been done in the intensive care unit (ICU) with favorable results; however, these studies had smaller sample sizes and limited external validity. While there is consensus on the superiority of CGM detecting hypoglycemic blood glucose levels, the effects on other patient outcomes in the critically ill remain uncertain.

4. Study Purpose:

The purpose of this study is to compare the use of CGM versus POC glucose monitoring in the critical care setting for differences in glycemic control and other important ICU outcomes.

5. Research Plan:

a. Study Design:

i. Prospective, single-center, randomized comparative trial

b. Study Sample:

- Adult patients at North Florida/South Georgia Veterans Health System anticipated to be admitted to an ICU for a minimum of 48 hours after enrollment
- A minimum sample size was calculated to be a total of 88 patients (44 per group), but will continue to enroll patients for a maximum of 2 years or a maximum of 300 patients
 - 1. Anticipated mean POC % time in range of 58% (based on current rates in our facility) with a standard deviation of 20%
 - 2. Anticipated mean CGM % time in range of 70% (based on CGM interpretation guidelines)
 - 3. 80% power, 5% alpha

c. Inclusion Criteria:

- i. Patients age 18-89

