- ii. Patients will be provided information on standards of care. As a participant in this study, all care including medical procedures, diagnostic tests, monitoring, medications, treatments, and other care will be the same for all patients as those who do not participate in the study, with the exception of the method of glucose monitoring.

f. Randomization:

- i. Study participants will be randomly assigned to one of the study groups after being found eligible for inclusion and giving consent to participate
- ii. A randomization process, such as a computerized algorithm or random number generator will be used to assign patients a group upon inclusion
- iii. Patients will be allocated 1:1 to the monitoring groups based on this randomization

g. Study Groups:

- i. Group 1: POC group (Blinded to CGM)
 - 1. All patients will have Dexcom G6 Pro CGM sensor/transmitter placed per device instructions
 - 2. Nurses and all members of the medical treatment team will be BLINDED to the CGM blood glucose readings during the study period
 - 3. Glycemic management will be based on POC glucose values.
- ii. Group 2: CGM group (Unblinded to CGM)
 - 1. All patients will have Dexcom G6 CGM sensor/transmitter placed per device instructions
 - 2. Nurses and all members of the medical treatment team will be UNBLINDED to the CGM blood glucose readings during the study period
 - 3. Glycemic management will be based on CGM values.

h. Study Outcomes

i. Primary Outcome

- Percentage of time in target range (BG 70-180mg/dL) [Appendix E]
 - a. Comparison of CGM readings between both types of monitoring/treatment groups

ii. Secondary Outcomes

- Percentage of time in each range (Appendix E) [Comparison of CGM readings between both types of monitoring/treatment groups]
 - a. Clinically significant hypoglycemic range (BG < 54 mg/dL)
 - b. Hypoglycemic range (BG 54-69 mg/dL)
 - c. Hyperglycemic range (BG 181-250 mg/dL)
 - Clinically relevant hyperglycemic range (BG >250 mg/dL)
- 2. ICU length of stay
- 3. ICU mortality
- 4. 30-day mortality

- 5. Costs associated with monitoring
- 6. Mean BG
- 7. Glucose variability for each group
 - a. % coefficient of variation = SD/mean BG*100%
- 8. Patient satisfaction

iii. Safety

- 1. Proportion of patients with a new infection
- 2. Proportion of patients with new AKI (AKIN guidelines)
- 3. Proportion of patients with CAM-ICU positive delirium
- 4. Proportion of patients with agitation (RASS \geq 2)

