- iii. Nursing staff will obtain a confirmatory POC for hypoglycemia alarms and administer appropriate therapy per protocol
 - 1. If a different reading is recorded, a venipuncture will be obtained
- iv. CGMs will record the BG and transmit to a remote device
 - The duration of CGM use for the study will be limited to 10 days (or the maximum duration allowable for use as recommended by the manufacturer)
- v. CGMs are pre-set with the following alerts:
 - 1. Low-glucose alerts set to 70 mg/dL
 - 2. Urgent low alerts set to 55 mg/dL, with urgent low soon alerts set if BG is expected to be 55 mg/dL within 20 minutes
 - 3. High alerts set to 250 mg/dL

- vi. BG readings less than 40 mg/dL are read on the CGMs as "LOW".While the exact reading will be unable to be determined, the amount of time spent in the "LOW" reading will be recorded
 - 1. When this occurs, a confirmatory POC reading will be obtained. If these numbers differ, a venipuncture will be collected

o. Data Collection

- i. CGM Sensor Data
 - 1. Clinical CGM data will be transmitted and evaluated using manufacturer software.
- ii. The following will be obtained from the Computerized Patient Records System (CPRS):
 - 1. **Demographic Data:** age, sex, race, weight, height, comorbidities
 - 2. Admission Data: length of stay, diagnoses, mortality
 - 3. Clinical Data: vital signs, complete metabolic panel (BMP) and other serum electrolytes (magnesium/phosphate), complete blood counts, liver function tests, infection/microbiology results (gram stains/cultures/sensitivities/PCR or other microbiology identification), blood gases, other laboratory data need to assess treatment/diagnoses/severity of illness, blood glucose levels, antidiabetic treatments (including type of insulin and doses administered), other medications (including presence of additional medications [e.g. steroids, vasopressors, or any other medications that may affect blood glucose or the CGMs sensors]), sedation/agitation (e.g. Richmond Agitation Sedation Scale) scores, delirium (e.g. CAM-ICU) scores, pain (e.g. CPOT, DVPRS) scores, diet/nutritional regimen
- iii. Satisfaction survey data: patient satisfaction survey
- iv. **Cost Analysis:** a comparison will be conducted based on the costs of equipment, staff time, and other relevant costs related to glucose monitoring in each group

p. Privacy, Security, and Confidentiality:

- i. Investigators will be responsible for maintaining patient privacy and confidentiality

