- ii. The principal investigator has the responsibility for security of the study
- iii. Study data will be entered, managed, and stored securely using VA Research Electronic Data Capture (REDCap).
- iv. Study data will be coded then de-identified for data analysis.

6. Analysis Methods:

Descriptive statistics and inferential statistical methods will be used as appropriate to report findings of this study.

To minimize risk of bias, data collection and analysis will be by performed by study team members not involved in the clinical care of the study participants, as possible.

7. Possible Discomforts and Risks:

- Inaccurate measurement of BG which could lead to hypo- and hyperglycemia
- CGMs are minimally invasive but could cause some patients mild physical pain or discomfort
- Apart from the type of monitoring utilized, no further changes to patient care will be made. Investigators will not alter medication prescribing to deviate from standard of care. As such, no additional discomfort or risk to the patient caused by this study is expected.

8. Possible Benefits:

- Reduction of serious hypoglycemia or other adverse events is the most relevant potential benefit of using CGM
- Decreased point-of-care finger sticks compared to standard care. This may lead to benefits such as increased patient comfort and reduced costs.
- Possible benefit of improved glycemic control with the ability to monitor glucose levels more carefully and adjust treatment as appropriate; this could lead to improved patient outcomes. We hypothesize the use of CGM will yield less cases of hypoglycemia and more glucose values at goal.

9. Anticipated Costs:

GGM devices and other necessary equipment will be provided through a manufacturer sponsored grant. Administrative and regulatory expenses will be covered by a manufacturer sponsored grant. No other costs beyond investigator salary and those for routine clinical care are anticipated.

10. Conflicts of Interest:

None of the investigators hold a patent or license for any material, object, or process involved with this research. None of the investigators own stock in or serve as consultants to any company involved in this research. The researchers will not receive payment or other financial incentive for conducting this study.

The PI or any of the Sub-investigators have no real or potential conflict of interest with regards to this research project.

11. References:

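### No trial-level safety review or pause criterion is described for the sensor-error harm that section 7 names, and the bedside checks act on one patient at a time

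*Combined protocol and SAP*

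**What the plan says.** Section 5.g says of the CGM group: "Glycemic management will be based on CGM values". Section 5.n.ii is fuller: it adds confirmatory POC readings where necessary and venipuncture. Section 5.b says the trial "will continue to enroll patients for a maximum of 2 years or a maximum of 300 patients".

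Section 7 lists "Inaccurate measurement of BG which could lead to hypo- and hyperglycemia" and then concludes: "As such, no additional discomfort or risk to the patient caused by this study is expected".

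The checks on the sensor are these:

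- Section 5.n.iii: "Nursing staff will obtain a confirmatory POC for hypoglycemia alarms and administer appropriate therapy per protocol". A venipuncture follows if the readings differ.
- Section 5.n.vi: the same sequence for a LOW reading (below 40 mg/dL).
- Section 5, Blood Glucose Correlation: calibration if necessary, and comparison with routine venipuncture at a daily interval. No size of disagreement is defined and no resulting action is stated.

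The POC group has scheduled POC tests: every 1 to 2 hours on an insulin infusion, at least 3 times a day on basal-bolus insulin (section 5.m.iii). Section 5.n gives the CGM group no such schedule, and section 8 expects fewer finger sticks.

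**The concern.** The method of monitoring is the intervention, and section 7 recognises that a wrong glucose value can harm. The harm is hardest to see when the sensor reads in range while true glucose is low. The alerts, including the predictive one, come from the sensor itself, so they may stay silent. One such event may look like a chance discordance to the treating nurse. Several, in different patients over many months, would be a device problem, and the plan gives nobody the task of putting them together.

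The final analysis is a weak backstop. The time-in-range outcomes, including the two hypoglycemic ranges, are computed from CGM readings (section 5.h), so a falsely high sensor would record a missed low as time in range. The safety outcomes in section 5.h.iii are infection, kidney injury, delirium, agitation and pain; none is sensor error. At stake is patient safety during a trial whose own records could show the pattern while enrolment is still open.

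**Working it through.** **1. The plan's own size.** Inputs from section 5.b: means 58% and 70%, SD 20%, 80% power, 5% alpha (taken as two-sided).

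n per group = 2 × (1.960 + 0.842)² × 20² / (70 − 58)² = 2 × 7.85 × 400 / 144 = 43.6, so 44 per group and 88 in total. This matches "A minimum sample size was calculated to be a total of 88 patients (44 per group"). The sample size is not in dispute.

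**2. Exposure.** At 1:1 allocation the ceiling is 300 / 2 = 150 CGM-group patients, which is 150 / 44 = 3.4 times the minimum.

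**3. Which check responds to which error (CGM group).**

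| Sensor | True glucose | Required confirmatory POC? | What else could reveal it |
|---|---|---|---|
| Low alarm or LOW | Not low | Yes, then venipuncture if different | – |
| Low alarm or LOW | Low | Yes | – |
| In range, no alarm | Low | No | Daily venous comparison, another reference test, clinical suspicion |

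**4. Review across patients.** Sections 1 to 11 and Appendices A to E contain no monitoring committee, periodic safety review, adverse-event procedure, discordance limit or pause criterion. Section 6 gives general analysis wording only. Yet the data exist: section 5.o collects sensor data and the glucose values in the patient record.

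**5. Scale, under assumed rates.** The documents give no rate. Let p be the assumed proportion of CGM-group patients with at least one detected event. Expected number = n × p; chance of at least one in the first 44 = 1 − (1 − p)^44.

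| p | Expected in 44 | Expected in 150 | At least one in first 44 |
|---|---|---|---|
| 5% | 2.2 | 7.5 | 90% |
| 10% | 4.4 | 15 | 99% |
| 15% | 6.6 | 22.5 | 99.9% |

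**6. What a periodic count could do (illustration only).** Suppose 5% is the acceptable rate, with a Beta(0.5, 9.5) prior. At each count, flag at the smallest k for which P(rate > 5% given k of n) exceeds 0.95. At n = 10, 20, ..., 150 this gives k = 3, 4, 5, 6, 6, 7, 8, 9, 9, 10, 11, 11, 12, 13, 13. Exact binomial recursion over the counts gives the chance of a pause:

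| Detected-event rate | Counts to 150 | Counts at 10, 20, 30, 44 |
|---|---|---|
| 5% | 10% | 4% |
| 10% | 81% | 33% |
| 15% | 99.5% | 70% |

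Two limits apply. The count at 150 comes when enrolment is complete, so it can prompt a review but no longer a pause. And the rates are of detected events: if reference tests catch an assumed half of true events, a true 10% becomes a detected 5%, and the chance over 150 falls from 81% to 10%.

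**The case against.** A reader might infer that a harmful sensor error would surface only at the final analysis. The documents do not support that. Alarms and LOW readings lead to a POC test, disagreement leads to venipuncture, and there is a daily venous comparison. Study team members are ICU clinicians who may also be treating the patient (section 5.e), so they may see discordances as they occur. It is only the pattern across patients that has no described route to attention.

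A reader might also infer that the trial cannot be paused. Silence is not a prohibition: nothing stops the principal investigator or the IRB from pausing, and a separate monitoring plan may exist outside these documents.

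Dependence on the sensor is also uncertain. Intravenous infusion is the preferred treatment (section 5.i.iii), and Appendix D has the nurse enter a POC glucose into the infusion tool. If that applies to the CGM group, reference values accompany infusion dosing and the blind spot narrows. Section 5.g says otherwise, so the point is unresolved. Subcutaneous dosing in that group is not covered by the Appendix D tool.

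Section 7's closing sentence might be read as meaning no risk beyond those just listed. If so, it should say that; as written, it sits against the harm listed above it.

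Finally, any numeric boundary is a reviewer's choice. It performs modestly at 44 patients and poorly if few events are detected, and a quiet count could then reassure falsely. That stands, and is why no boundary is prescribed here.

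**Conclusion.** The concern holds in this form: the documents describe no trial-level safety review or pause criterion for the harm section 7 names; the bedside checks are per patient, have no discordance limit, and are not said to be pooled during the trial. A pattern of sensor-missed hypoglycemia could go unseen until the end, over as many as 2 years and about 150 CGM-group patients. The documents do not support saying that individual errors would go unseen or that a pause is impossible.

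The size cannot be fixed from the documents. The event counts and pause probabilities rest on assumed rates of detected events, an assumed acceptable rate and an example boundary. The gap itself rests on none of these. It is a worthwhile, inexpensive improvement in patient safety; it does not affect the sample size or the primary comparison. Confidence is moderate, chiefly because a separate monitoring plan may exist and the role of POC values in infusion dosing is unclear.

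**What to change.** 1. **Add a pooled safety count.** At a set interval, for example after every 10 CGM-group patients, have the team members whom section 6 keeps apart from clinical care pool the paired sensor and POC or venous values. Count CGM-group patients with a reference glucose below 54 mg/dL while the time-matched sensor value was 70 mg/dL or more; both limits are the protocol's own. State the matching window, and report the number of reference pairs so that a low count from few tests is not mistaken for safety. Report to the principal investigator and the IRB against a limit the investigators set in advance. If a separate monitoring plan already does this, cite it.
2. **Correct section 7** so that its closing sentence agrees with the risk listed above it.
3. **Reconcile section 5.g with Appendix D** on which glucose value drives infusion dosing in the CGM group. This review does not say which is right.

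The cost is a short amendment and at most 150 / 10 = 15 counts from data already collected. The count compares no groups, so it spends none of the 5% alpha. The downside is an occasional unnecessary review or pause: under the example boundary with a detected rate of 5%, about 10% of trials over 150 CGM-group patients and 4% at 44.

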Appendix A. Weight-Based SC Insulin Dosing – PO diet eating full meals

- Age > 70 years, eGFR <60mL/min, underweight, risk for hypoglycemia
 - Total Daily Insulin Dose = 0.2 units/kg
 - 0.1 unit/kg/day basal glargine
 - 0.03-0.05 units/kg/meal nutritional aspart
 - Correctional Aspart AC = Low (1 unit:50 mg/dL BG >150 mg/dL)
- Normal Body Weight (BMI 18.5-25)
 - Total Daily Insulin Dose = 0.4 units/kg
 - 0.2 unit/kg/day basal glargine
 - 0.07 units/kg/meal nutritional aspart
 - Correctional Aspart AC = Low (1 unit:50 mg/dL BG >150 mg/dL)
- Overweight or Obese (BMI >25)
 - Total Daily Insulin Dose = 0.5 units/kg
 - 0.25 unit/kg/day basal glargine
 - 0.08 units/kg/meal nutritional aspart
 - Correctional Aspart AC = Medium (2 units:50 mg/dL BG >150 mg/dL)

Additional Considerations:

- Aspart dose should be given immediately prior to meal. If it is unknown if patient will eat, hold aspart prior to meal and give after meal if patient consumes at least 50%. Give aspart dose within 15 minutes of first bite.
- If patient is expected not to eat or consumes less than 50% of meal: nurse to notify physician, hold scheduled nutritional aspart dose, continue basal glargine, and give aspart correctional sliding scale.
- Correctional aspart to be given in addition to nutritional aspart dose.
- If blood glucose is less than 100 mg/dl, nurse to hold nutritional/correctional insulin and notify physician. Basal insulin should be continued as prescribed unless instructed otherwise by physician orders.
- If patient has abrupt change in diet (e.g. made NPO for urgent procedure), nurse to notify physician. It is recommended to start dextrose containing IV fluids and continue basal insulin glargine to prevent rebound hyperglycemia. Insulin regimen should be re-evaluated by provider as warranted.
- Pre-meal blood glucose goal is 100-150 mg/dl.

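### Appendix A, first tier: with three dosed meals a day, the upper part of the per-meal insulin range exceeds the tier's stated total daily dose, by up to 25%

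*Combined protocol and SAP*

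**What the plan says.** Appendix A sets out weight-based subcutaneous insulin for patients eating full meals. Its first tier prints three figures:

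- the total: "Total Daily Insulin Dose = 0.2 units/kg"
- the basal part: "0.1 unit/kg/day basal glargine"
- the mealtime part: "0.03-0.05 units/kg/meal nutritional aspart"

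The other two tiers each give a single mealtime value: "0.07 units/kg/meal nutritional aspart" with a total of 0.4 and basal of 0.2 units/kg, and "0.08 units/kg/meal nutritional aspart" with a total of 0.5 and basal of 0.25 units/kg. Only the first tier has a range. Appendix A does not state the number of meals per day.

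The notes below the tiers treat correctional insulin as extra: "Correctional aspart to be given in addition to nutritional aspart dose". They also limit exposure. At low glucose the instruction is "If blood glucose is less than 100 mg/dl, nurse to hold nutritional/correctional insulin and notify physician", and if the patient is not expected to eat, or eats less than half a meal, the nurse is to "hold scheduled nutritional aspart dose".

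Section 5.i leaves the subcutaneous regimen to the treating ICU team and refers to Appendices A to C as recommended dosing.

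**The concern.** A total printed beside its components should be recoverable from them. In this tier, basal insulin takes half the total and leaves 0.1 units/kg/day for meals. Three meals at the top of the range use 0.15 units/kg, half as much again as that remainder. A clinician working from the total and one working from the per-meal line could reach different daily doses for the same patient.

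The tier is defined in part by risk of hypoglycemia, so a figure that can run above its own stated total matters more here than elsewhere in the table. What is at stake is the consistency of the dosing guidance. The table applies to both arms, so the point does not bias the comparison or bear on the sample size.

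**Working it through.** **Inputs.** All doses are the Appendix A and Appendix C figures, in units/kg. The number of dosed meals, *n*, is not given, so it is taken as 3, with 2 and 4 shown as a range. Correctional insulin is left out because it is additional and has no fixed daily amount.

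**Formula.** Daily sum = basal + *n* × per-meal dose, compared with the stated total.

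**Where the stated 0.2 is recovered.** At *n* = 3 it needs (0.2 - 0.1)/3 = 0.033 per meal; at *n* = 2 it needs (0.2 - 0.1)/2 = 0.05. Both values lie in the printed range, but they belong to different meal counts. (This is arithmetic only, not a proposed dose.)

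**First tier, stated total 0.20**

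| Meals | At 0.03 per meal | At 0.05 per meal |
|---|---|---|
| 2 | 0.1 + 0.06 = 0.16 (-20%) | 0.1 + 0.10 = 0.20 (0%) |
| 3 | 0.1 + 0.09 = 0.19 (-5%) | 0.1 + 0.15 = 0.25 (+25%) |
| 4 | 0.1 + 0.12 = 0.22 (+10%) | 0.1 + 0.20 = 0.30 (+50%) |

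At three meals every per-meal value above 0.033 exceeds the total. That is (0.05 - 0.033)/(0.05 - 0.03), or about five sixths of the printed range.

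**Which meal count does the appendix use?** The other two tiers give a test.

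| Meals | Second tier, stated 0.40 | Third tier, stated 0.50 |
|---|---|---|
| 2 | 0.2 + 0.14 = 0.34 (-15%) | 0.25 + 0.16 = 0.41 (-18%) |
| 3 | 0.2 + 0.21 = 0.41 (+2.5%) | 0.25 + 0.24 = 0.49 (-2%) |
| 4 | 0.2 + 0.28 = 0.48 (+20%) | 0.25 + 0.32 = 0.57 (+14%) |

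Solved the other way, the implied counts are 0.2/0.07 = 2.9 and 0.25/0.08 = 3.1 meals. Only three fits both tiers.

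**Is it rounding?** Appendix C gives nutritional insulin every 6 hours, so four doses a day. Its tiers sum to 0.1 + 4 × 0.025 = 0.20 (exact), 0.2 + 4 × 0.05 = 0.40 (exact) and 0.25 + 4 × 0.06 = 0.49 against 0.5 (-2%). The first of these has the same total and basal dose as the tier in question. Every other split tier in Appendices A and C therefore closes within 2.5%; the 25% here is ten times that.

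**Size in units at three meals (illustrative weights).** At 50 kg: 9.5 to 12.5 against 10 units/day, so at most 2.5 over, or about 0.8 per meal. At 80 kg: 15.2 to 20 against 16 units/day, so at most 4 over.

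**The case against.** The strongest reply is that no two printed figures conflict by themselves: the mismatch needs a meal count that the appendix does not supply. At three meals the stated 0.2 lies inside the range, and at two it equals the top. The range may have been built that way, since 0.1/3 = 0.033 (0.03 when rounded) and 0.1/2 = 0.05 are the mealtime share spread over three and two meals. On that reading the total governs and nothing is wrong.

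That reading is possible, and it means an authors' error is not proven. But the document does not state it, the appendix is for patients eating full meals, and the other two tiers fit only three. As printed, 0.05 at each of three meals is allowed. Counting correctional insulin in the total would widen the gap.

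Indirect support for three meals from section 5.m (glucose checks at least three times daily on a basal:bolus regimen) is weak. It is a minimum testing frequency, given for the POC group only, and the conclusion does not rest on it.

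The objection to practical reach largely stands. Section 5.i prefers intravenous insulin, recommends the subcutaneous regimen only for hemodynamically stable patients on consistent nutrition, and leaves daily adjustment to the treating team. The hold rules limit exposure further.

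**Conclusion.** The concern holds, as a minor inconsistency. Assuming three dosed meals a day, the first-tier components sum to 0.19 to 0.25 units/kg against a stated 0.2, or -5% to +25%. The low end is rounding; the top is not. The conclusion depends on the meal count, which is an assumption supported by the fit of the other two tiers. With two meals the excess disappears; with four the components exceed the total throughout the range (+10% to +50%).

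The arithmetic is certain, but the authors' intention is not known. The consequence is confined to discretionary dosing guidance for a subset of patients. Design, primary outcome and sample size are unaffected.

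**What to change.** Amend one line of the first tier of Appendix A. Either reconcile the stated total with the basal and per-meal components, or state the number of dosed meals per day at which they agree. If the range was meant to cover different meal counts, a short clause saying so resolves the point. The sponsor's clinical team must decide which figure stands; this review takes no position on the dose. No statistical work is needed.
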